3.1 Anticipated Clinical Benefits

While there are no direct benefits to the subject's participating in the study, participation will provide information about the study device that could benefit other women in the future.

3.2 Anticipated Adverse Events and Adverse Device Effects

Per the device instructions for use, there are risks associated with hysteroscopy and use of the Cytuity™ device.

Additionally, in this study, there are risks associated with general anesthesia as the patient is scheduled to undergo general anesthesia for their scheduled salpingo-oophorectomy and/or salpingectomy.

Risks related to anesthesia or hysteroscopy include:

- Nausea / vomiting
- Dizziness / light headedness

Risks related to hysteroscopy include:

- Cramping
- Bleeding/spotting
- Vaso-vaginal response
- Hypervolemia
- Infection
- Perforation of the uterus or fallopian tubes, with possible injury to bowel, bladder, or surrounding blood vessels.

Table 1. Potential Adverse Events related to the Cytuity™ device and Mitigation Strategy

Risk	Mitigation
Perforation of the fallopian tube is a risk because of its tortuosity and narrow dimensions.	a. No rigid portion of the device enters the fallopian tube. Instead, a very small balloon (less than 1 mm diameter) is everted through the tube. Because the balloon is self-navigating, the eversion of the balloon will minimize the physician’s manual advancement of the device through the tube and therefore the risk of perforation is expected to be minimized. b. A salpingo-oophorectomy or salpingectomy will be performed directly after the Cytuity™ device procedure.
A foreign object will be introduced into the subject and therefore infection may occur.	c. A sterilized device will be supplied to the physician. d. The device instructions for use mandate sterile technique.
This study could prolong the time the subject is under general anesthesia by an estimated 5-7 minutes per Cytuity™ device use.	e. Prior to the study, the physician will be trained on the bench on how to use the Cytuity™ device accurately and in an efficient manner, therefore minimizing overall time of the procedure.

3.3 Risk Mitigation

Subjects participating in the study are already scheduled to undergo salpingo-oophorectomy or salpingectomy with the attendant risks of that surgery. Any events that occur as a result of the planned surgery will be medically managed by the subject's physician per the institution's standard of care. The study device and procedure present minimal additional risk to subjects participating in this study, since the contacted anatomy will usually be removed from the subject immediately after study device use and because the device is FDA cleared for cell collection from the fallopian tube. Standard risks associated with hysteroscopic instruments include perforation, infection and bleeding. It is not expected that the Cytuity™ device is associated with any increased risks as compared to commercially available hysteroscopic instruments. The Cytuity™ device procedure will increase the amount of time that the subject is under general anesthesia by an estimated 5-7 minutes per Cytuity™ device use. Additional Cytuity™ risks and mitigations are noted in Table 1 above. There is the potential that unknown risks exist.

This investigation will be conducted by investigators that are qualified by training and experience in the treatment of patients presenting for salpingo-oophorectomy or salpingectomy. Adequate measures including eligibility criteria limitations, subject screening and pre-visit assessment of their health condition have been incorporated into the clinical investigation to minimize such risks.

Investigators are also familiar in the use of hysteroscopes or have gone through the sponsor's training module.

3.4 Risk-to-Benefit Rationale

The sponsor believes that any potential risks presented by this investigation have been minimized and that the overall residual risk is deemed acceptable.

The study device and procedure present minimal additional risk to subjects participating in this study, since the contacted anatomy will be removed from the subject immediately after study device use.

4 Objective

The primary objective of the study is to evaluate the sensitivity and specificity, estimated to be 80% and 90% respectively, of cytological evaluation of samples collected by the Cytuity™ device in determining the presence or absence of malignant cells that originated in the fallopian tube or malignant cells that have migrated to the fallopian tubes. The results obtained from the cytological samples will be compared against the results

obtained from the gold standard. The gold standard is the surgical histology (pathology) assessment of the fallopian tubes, and in cases of malignant cell migration, the ovaries.

5 Design of the Clinical Investigation

5.1 General

This clinical investigation is a prospective, multi-center, non-randomized study. Subjects will be recruited from a population of women who are already scheduled to undergo salpingo-oophorectomy or salpingectomy. The study protocol requires hysteroscopic sampling of the fallopian tube with the Cytuity™ device immediately prior to the scheduled surgery.

Cytology results from the cells collected using the Cytuity™ device will be independently evaluated at two pathologists. Concordant and/or adjudicated cytology results are compared to the site's surgical histology results from the removed tissue(s).

Pathology results (histology) will not be shared with pathologists conducting cytology evaluations and cytology results will not be shared with the site or the pathologist evaluating histology evaluations to remove bias. Additionally, cytology results will not be shared with the study's subjects or investigator as no medical decisions will be made based on Cytuity™ results.

Any baseline testing, pathology (histology) evaluations, and all other clinical care will be in accordance with each participating institution's standard of care for patients undergoing salpingo-oophorectomy or salpingectomy.

5.2 Participants

The study population will include participants presenting with a pelvic mass suspicious for malignancy who are already scheduled to undergo a salpingo-oophorectomy or salpingectomy. Screening of these participants is done to determine if they meet inclusion and exclusion criteria.

5.2.1 Inclusion Criteria

A participant may be enrolled in this study if she meets all of the following criteria:

1. Subject is medically cleared for surgery
2. Subject is scheduled to undergo salpingo-oophorectomy or salpingectomy for a pelvic mass suspicious for malignancy
3. Subject must be 18 years of age
4. Subject must be able to provide informed consent

5.2.2 Exclusion Criteria

1. Contraindication to hysteroscopy
3. Acute pelvic inflammatory disease
4. Active or recent lower pelvic infection
5. Pregnancy
6. Delivery or termination of a pregnancy in the past 6 weeks
7. Known tubal obstruction
8. Tubal ligation
9. Invasive carcinoma of the cervix or endometrium
10. Intolerance of anesthesia

5.2.3 Screen Failures and Enrollment

Any individual participant that fails to meet inclusion and exclusion criteria is considered a screen failure.

Screen failures can occur prior to enrollment or after enrollment. Screen failures that occur prior to enrollment are logged but no other study data is collected or analyzed. A participant is considered enrolled in the clinical investigation after she has provided written informed consent.

When an enrolled subject fails to meet inclusion and exclusion criteria, no additional data beyond baseline and reason for screen failure need be collected.

5.2.4 Analysis Data Sets

An enrolled subject may voluntarily withdraw consent at any time during the study. Additionally, enrolled subjects may be withdrawn by the investigator (e.g. if the investigator determines hysteroscopy will not be attempted). The reason for withdrawal will be documented.

Once the subject is enrolled, the hysteroscope is placed and ostia identified, the subject is part of the intent to treat (ITT) population. Subjects may still be screen failures after hysteroscopic visualization of the ostia if they fail any other eligibility criteria such as discovery of tubal ligation. Screen failures are not part of the ITT data set but are part of the enrolled data set.

The modified intent to treat (mITT) population are those subjects with an adequate Cytuity™ cell sample. Primary and secondary endpoints will be evaluated using this mITT population.

5.2.5 Enrollment Duration

The enrollment period is expected to take approximately 12 months.

5.2.6 Total Expected Clinical Investigation Duration

Recruitment of this study is expected to take approximately 12 months followed by data analysis. Individual study participation is approximately 1 day after the study procedure.

5.3 Procedures

5.3.1 Consenting Visit or Contact

Patient charts (medical history, including pregnancy test for females of child bearing potential) will be previewed for study eligibility, but no study-specific information will be collected on study case report forms before informed consent.

It is typical to ensure that prior to performing the salpingo-oophorectomy or salpingectomy, the subject is tested for pregnancy (for females of childbearing potential). This test is therefore part of the standard of care.

If the subject meets all pre-procedure eligibility criteria and agrees to participate in the study, written informed consent will be obtained.

[figure not shown]
Medical history and demographics related to the study procedure are collected on case report forms following informed consent.

5.3.2 Study Treatment

Cytuity™ procedures for collection of cells from the fallopian tube will be performed immediately prior to the scheduled salpingo-oophorectomy (S-O) or salpingectomy.

As shown in Figure 2, the device is comprised of a catheter and a handle. The catheter includes a balloon, a shaft (which is made up of a stainless steel tube and a Nylon tube), a sheath, and a sheath knob. The handle includes a drive wheel and a Luer in the handle body. The Luer attaches to a commercially available inflation device via a stopcock supplied with Cytuity™.

Figure 2. Cytuity™ device

Outside the body, the Cytuity™ device is prepared by pressurizing the balloon and pre-extending the sheath and balloon 1.5cm.

The Cytuity™ device is pressurized using a commercially available inflation device that is attached to the device Luer. The sheath knob is then advanced approximately 1.5cm forward to the preparation mark. By rotating the drive wheel, the balloon is then extended forward until the tip of the balloon aligns with the tip of the extended sheath. The preparation is complete and the inflation device is then removed.

Just prior to the scheduled S-O or salpingectomy surgery, the physician inserts the hysteroscope into the subject and visualizes the tubal ostia. Upon successful visualization, the prepared Cytuity™ device is inserted into the working channel of the hysteroscope until the distal tip of the catheter is positioned immediately proximal to the ostium of a fallopian tube. The handle is advanced to cannulate the ostium with the pre-extended balloon. Then the balloon is further advanced into the fallopian tube by rotating the drive wheel.

Cells are collected from the fallopian tube on the surface of the balloon. Then the balloon is deflated by relieving pressure using the stopcock. The device is then retracted into the sheath and removed from the working channel of the hysteroscope and from the subject. Alternatively, the hysteroscope may remain in the subject for cell collection at the contralateral tubal ostium. A second Cytuity™ device is used for the second collection. Upon each Cytuity™ device removal from the subject, both balloon and sheath (distal tip) are to be simultaneously cut off and immersed into cytopreservative by stirring to agitate the cells. The vial is labeled with the unique subject's study ID#, and "L" for left or "R" for right tube.

Complete instructions are provided in the Cytuity™ device instruction for use (DFU) provided with each study device.

Following Cytuity™ use, the hysteroscope is removed. The surgical instrumentation can then be placed and the subject proceeds to the planned surgery.

A cytology specimen log will be completed to show transfer of the vials from the site either directly to the cytology core lab or to the sponsor as an interim provider of transport to the cytology core lab.

Samples may be stored at room temperature pending transfer if needed.

5.3.3 Prior to Study Exit

Subjects are exited 24 hours post- Cytuity™ use or at discharge, whichever occurs first. The only time the follow-up period is extended is if the subject has a Cytuity™ study or device-related adverse event. In these instances, the subject is followed until the investigator deems the adverse event is resolved or for 30 days, whichever comes first.

The following data is collected at the day of study exit:

- Any adverse events up to study exit
- The reason for study exit (e.g. completion of the study)

The subject has no additional visits or follow-up required. See Table 2.

Table 2. Schedule of Assessments

	Screening / Informed Consent	Cytuity™ Study Procedure/ Salpingo-oophorectomy or salpingectomy	Subject Study Exit	Lab Test Results (no subject involvement)
Window (days)	-21	0	+1*	NA
Medical History, including review of pregnancy status (for women of child bearing age)	X			
Demographics	X			
Inclusion / exclusion criteria determination	X			
Informed Consent	X			
Pregnancy Test**	X			
Cell Collection using Cytuity™ device		X		
Adverse Events		X	X	
Cytology and Surgical Histology Results				X

*Unless a Cytuity™ study or device related AE occurs, in which case the AE will be followed until resolution or for 30 days, whichever comes first.

**Pregnancy test must be within 21days of study procedure.

5.3.4 Post-Operative Pathology

Per site standard procedures, excised tissue will be sent to site-specific pathology department/facility. The histological evaluation will include standard of care only (including micro-sectioning of the fallopian tubes); no different, unique or experimental methods will be used.

Transfer of each subject's surgical pathology (histology) report diagnostic data is a study requirement. All protected health information will be redacted by the site and the report will be labeled with the subject's study identification number. The redacted histology report will be provided to the sponsor. The redacted report will be reviewed by an independent study pathologist who will complete the study histology case report form. The study pathologist reviewing histology may contact the site's surgical pathology lab for clarification of the redacted report if warranted. If clarification is required, all communications between the site pathology lab and the study pathologist reviewing histology must be attached to the redacted report and included in the study data.

The study pathologist will use the redacted site pathology report to document the histology results of fallopian tube malignancy, ovarian malignancy, and other malignancy on a study case report form.

5.3.5 Post-operative Cytology

Cytuity™ collected cytology samples will be delivered to the sponsor and then the core lab for slide preparation.

The core lab will be responsible for logging in received samples and processing the samples into slides. This requires a centrifugation step and the creation of a monolayer preparation on a microscope slide with the recovered fallopian tube cells. The slide will be stained to make the cells visible using the Pap stain method. The slide(s) are then transferred to Pathologist #1. Pathologist#1 will review and interpret the slides for evidence of malignancy.

Pathologist #1 will document the cytology results of the fallopian tube samples on a study case report form for sponsor review. The sponsor will then forward the slide(s) labeled with the patient study ID number to pathologist #2. The 2nd pathologist will review and interpret the slides for evidence of malignancy. Pathologist #2 will document the cytology results of the fallopian tube samples on a study case report form for sponsor review. The slide(s) are returned to the sponsor.

The sponsor will review the results between pathologist #1 and pathologist #2 for concordance. If the results are in agreement (concordant), the sponsor will compare the concordant cytology results with the surgical histology/pathology results. If the cytology results are not in agreement (discordant), the sponsor will arrange for pathologist #3 to adjudicate. The adjudicating pathologist will review and interpret the slide(s) for evidence of malignancy. He/she will likely agree with either pathologist #1 or #2, ultimately providing the final cytology result. The results will be recorded on a CRF. The adjudicating pathologist's interpretation is

final. The slide(s) and CRF are returned to the sponsor for final comparison to the independent pathology (histology) case report forms.

5.3.6 Activities Performed by Sponsor or Sponsor Representatives

The sponsor or designee will conduct all site investigator training, site staff training, core lab training, study pathologist training and site initiation visits.

One or more representatives of the sponsor may be present during the study procedure at the request of the investigator and under supervision of the investigator to assist with device preparation prior to subject use; to assist with collecting holding the cell collection vial after subject use; and secure sample transfer to the cytology core lab post subject use.

The sponsor may transfer cytology samples from the sites to the core cytology lab and then to and from pathologists reviewing cytology slides. The site's histology lab and study pathologist reviewing histology are blinded to the results of the cytology core lab and the pathologists reviewing cytological slides.

The sponsor or designee will monitor sites as detailed below in the section titled Monitoring Plan.

The sponsor will complete all data review, statistical analysis, and write the final study report.

Boston Scientific personnel will not do the following:

- Practice medicine.
- Provide medical diagnosis or treatment to subjects.
- Discuss a subject's condition or treatment with a subject.
- Independently collect critical study data (defined as primary or secondary endpoint data).
- Enter data in electronic data capture systems or on paper case report forms.

5.4 Monitoring Plan

Study site monitoring will be performed by qualified monitors who may be employees or consultants to the sponsor or a qualified CRO selected by the sponsor.

Each site will be visited regularly in an effort to ensure that the study is conducted in compliance with the study protocol and all applicable guidelines, laws and regulations.

To monitor, study visits may include, but are not limited to, the review of device supply, presence of required documents, the informed consent process, and comparison of CRFs with source documents found in the subject's medical records. Monitoring will also include the assessment of the site's overall progress, including but not limited to the site's ability to keep accurate records and to report study related data to the study sponsor in a timely fashion.

The investigator agrees to participate in study visits conducted at a reasonable time, in a reasonable manner.

In addition to study related logs, plans, and IRB approved documents (protocol, informed consent, etc.), investigators must maintain information in the study subject's medical records to corroborate data collected on the CRFs. This ensures the validity of the study data collected and is used by the sponsor or designees to monitor the study.

Data / CRF corrections and/or ambiguous data points may be resolved in person during monitoring visits, via data clarification forms (DCFs) provided to the site, and/or data queries. Findings of non-compliance and/or deviations from the protocol shall be reviewed with the investigator(s) and disclosed in a written monitoring report. The sponsor shall then either secure compliance or may discontinue shipments of the device to the investigator until compliance is achieved and/or terminate the investigator's participation in the investigation.

6 Statistical Considerations

6.1 Hypothesis

As sensitivity is a function of diseased fallopian tubes only, while specificity is a function of non-diseased fallopian tubes, the statistical hypotheses for sensitivity and specificity are considered to be independent. Each hypothesis is framed as a 1-sided test with a type I error rate of 2.5%.

For sensitivity, the following hypothesis will be tested:

H_{Null} : Sensitivity \leq 60% versus

$H_{Alternative}$: Sensitivity $>$ 60%

For specificity, the following hypothesis will be tested:

H_{Null} : Specificity \leq 70% versus

$H_{Alternative}$: Specificity $>$ 70%

6.2 Primary Outcome

The primary endpoint of the study is to evaluate the sensitivity and specificity of the cytological samples collected from the fallopian tube in determining the presence or absence of malignancy for fallopian tube involvement as compared to the current gold standard, the surgical pathology (histology) results.

Fallopian tube involvement is defined as:

1. Malignant cells that originated in the fallopian tube. This is detected by the surgical histology results from the fallopian tube.
2. Malignant cells that have migrated to the fallopian tube. This can be detected by surgical histology results of the ovaries or fallopian tubes.

The site's pathology report will contain the surgical histology evaluation of the removed fallopian tube specimens. These results will be compared to corresponding results from cytologic evaluation of fallopian tube samples. Sensitivity and specificity will be calculated for the Cytuity™ device as compared to surgical histology of the ovaries and fallopian tube for fallopian tube involvement.

Note that in most cases where malignant cells have migrated into the fallopian tube from the ovary, fallopian tube histology can be used to confirm presence of malignancy in the fallopian tube as outlined in #2 above. However, due to washing required for specimen preparation, in some cases fallopian tube histology may be negative although malignant cells *may have been present*. That is, malignant cells may have been washed out. Therefore, when the histology of the tube is negative, but the histology of the same sided ovary is positive and the cytology results of the fallopian tube are positive, this result will be categorized as a true positive. This finding will be called 'favorable discordance' relative to cytology results.

The following formulas will be used to determine sensitivity and specificity:

$$\text{sensitivity} = \frac{\text{number of true positives}}{\text{number of true positives} + \text{number of false negatives}}$$

$$\text{specificity} = \frac{\text{number of true negatives}}{\text{number of true negatives} + \text{number of false positives}}$$

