6.3 Secondary Outcomes

The secondary endpoints will include the following:

- Positive Predictive Value (PPV), Negative Predictive Value (NPV), and Diagnostic Accuracy will be calculated for Cytuity™ as compared to surgical histology of the ovaries and fallopian tube for fallopian tube involvement.
- Sensitivity, specificity, PPV, NPV, and accuracy will be calculated for Cytuity™ as compared to surgical histology of the fallopian tube.
- Sensitivity, specificity, PPV, NPV, and accuracy will be calculated for Cytuity™ as compared to surgical histology of the ovaries for epithelial malignancies.*
- Sensitivity, specificity, PPV, NPV, and accuracy will be calculated for Cytuity™ as compared to surgical histology for fallopian tube involvement for subject level analysis.

*Epithelial cancers, which consist of high and low-grade serous carcinomas, endometrioid, clear cell and mucinous subtypes make up approximately 95% of all ovarian cancers.

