6.5 Statistical Methods

This trial was designed with formal statistical hypotheses for both sensitivity and specificity. The sample size was determined based on a fallopian tube-level (each tube will be considered a data point), and assuming a high correlation of 75% between tubes in individual subjects. Previous data suggest that when 1 fallopian tube is positive for malignancy, the subject's other tube is positive about 75% of the time so making a total correlation of 75% is a reasonable assumption.

Since sensitivity is a function of diseased tubes only, while specificity is a function of non-diseased fallopian tubes, the statistical hypotheses for sensitivity and specificity are considered to be independent. Each hypothesis is framed as a 1-sided test with a type I error rate of 2.5%.

For sensitivity, the following hypothesis will be tested:

HNull: Sensitivity \leq 60% versus
HAlternative: Sensitivity $>$ 60%

For specificity, the following hypothesis will be tested:

HNull: Specificity \leq 70% versus
HAlternative: Specificity $>$ 70%

For the sample size calculation, the expected sensitivity of the Cytuity™ device is approximately 80% and the expected specificity is approximately 90%. Based on these parameters and requiring $>$ 80% power for both hypotheses above, 32 subjects positive for malignancy and 18 subjects negative for malignancy are required.¹⁴

Since this is a prospective study in which it is anticipated that the number of subjects testing negative will far exceed subjects testing positive, the sample size calculation is driven by the requirements for the sensitivity hypothesis. Conversion from subjects to fallopian tubes yields a requirement of 56 tubes positive for cancer.¹⁵ Based on an assumed 20% prevalence rate of (subject-level) malignancy, a sample size of 140 subjects (280 tubes) in which both fallopian tubes are tested is statistically likely to produce at least the 56 positive tubes required.

Because the primary analysis is based on fallopian tubes, the analysis must account for the subject-level correlation.¹⁶ A Logistic random-effects model will be used to calculate the point estimates and 95% (2-sided) confidence intervals for sensitivity and specificity.^{17,18} The adjustment proposed by Obuchowski will be performed for comparison.¹³

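### The primary reference standard in section 6.2 depends on the cytology result it is meant to judge, and the opposite case (same histology, negative cytology) has no stated class

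*Combined protocol and SAP*

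**What the plan says.** Section 6.2 defines fallopian tube involvement as malignant cells that arose in the tube or that migrated to it. For migration it adds: "This can be detected by surgical histology results of the ovaries or fallopian tubes". Section 4 (Objective) puts it this way: "The gold standard is the surgical histology (pathology) assessment of the fallopian tubes, and in cases of malignant cell migration, the ovaries".

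Section 6.2 then makes an exception, on the ground that specimen washing may remove malignant cells before histology. It applies "when the histology of the tube is negative, but the histology of the same sided ovary is positive", and if in addition "the cytology results of the fallopian tube are positive, this result will be categorized as a true positive". The plan labels this favorable discordance. No section classifies a tube with the same two histology findings and negative cytology.

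Section 5.1 states a safeguard for the readings: "cytology results will not be shared with the site or the pathologist evaluating histology evaluations to remove bias". Under section 5.3.4 the study pathologist, working from the redacted site report, will "document the histology results of fallopian tube malignancy, ovarian malignancy, and other malignancy on a study case report form". Section 6.3 plans secondary analyses against tube histology alone ("as compared to surgical histology of the fallopian tube") and against ovarian histology for epithelial malignancies. Section 6.1 tests sensitivity against 60% and specificity against 70%, each one-sided at 2.5%.

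**The concern.** A reference standard should be settled without the test under evaluation. Here positive cytology is one of the three conditions that make the tube a true positive. A tube with this histology therefore cannot be a false positive. If its negative-cytology counterpart remains a true negative, it cannot be a false negative either, and every tube of this kind counts as correct whatever cytology shows.

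The washout rationale does not support a one-sided rule. Loss of cells during preparation happens to the histology specimen and does not depend on the cytology result. If it justifies relying on the ovary when cytology is positive, it does so equally when cytology is negative.

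Both primary hypotheses rest on this classification. So do the secondary predictive values, accuracy and subject-level results that use the involvement definition. Blinding of readers does not help, because the dependence enters afterwards, when the two results are combined.

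**Working it through.** **The plan's own figures.** With variance at the alternative, n = (1.960 + 0.842)² × p₁(1 − p₁)/(p₁ − p₀)².
- Sensitivity: 7.849 × 0.16/0.04 = 31.4, so 32 subjects.
- Specificity: 7.849 × 0.09/0.04 = 17.7, so 18 subjects.
- Tubes: 32 × (1 + 0.75) = 56, using the 75% correlation of section 6.5.

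The stated figures reproduce. The problem lies in which tubes are counted as diseased.

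**Notation.**
- T: tubes with positive tube histology; a of them are cytology-positive.
- D: tubes with negative tube histology and a malignant same-side ovary; q is their cytology-positive rate.
- C: all other tubes; s is the specificity in them.

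| Reference | Sensitivity | Specificity |
|---|---|---|
| As written, plain reading | (a + Dq)/(T + Dq) | (Cs + D(1−q))/(C + D(1−q)) |
| Tube or same-side ovary | (a + Dq)/(T + D) | s |
| Tube only | a/T | (Cs + D(1−q))/(C + D) |

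**Direction.** Against tube-only, the rule adds Dq to both numerator and denominator of a proportion, which cannot lower it. Against the composite, the numerator is the same and the denominator is no larger. The same two steps apply to specificity. No assumed value is needed.

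**Size, sensitivity.** The documents give neither D nor q, so these are assumptions: T + D = 56 and a/T = 60%, the null value. Tube-only sensitivity is then 60% in every row. Exact rejection is the probability that the Clopper-Pearson lower 97.5% bound exceeds 60%, averaged over the binomial number of cytology-positive D tubes, with tubes independent; at D = 0 it is 1.4%.

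Clustered rejection comes from 200,000 simulations of 28 subjects with two tubes each, rejecting when the Obuchowski-adjusted 95% interval lies above 60%. At D = 0 it is 3.9%, and for tube-only histology it is 3.0–4.3%.

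| T/D | q | As written | Composite | Exact rejection | Clustered rejection | Expected positive tubes, T + Dq |
|---|---|---|---|---|---|---|
| 46/10 | 60% | 64.6% | 60.0% | 7.1% | 10.3% | 52.0 |
| 36/20 | 60% | 70.0% | 60.0% | 23.3% | 27.8% | 48.0 |
| 28/28 | 60% | 75.0% | 60.0% | 49.0% | 56.4% | 44.8 |
| 46/10 | 30% | 62.4% | 54.6% | 3.8% | 6.9% | 49.0 |
| 36/20 | 30% | 65.7% | 49.3% | 7.9% | 13.2% | 42.0 |
| 28/28 | 30% | 69.2% | 45.0% | 14.5% | 24.1% | 36.4 |
| 46/10 | 10% | 60.9% | 51.1% | 2.2% | 5.0% | 47.0 |
| 36/20 | 10% | 62.1% | 42.1% | 2.8% | 6.7% | 38.0 |
| 28/28 | 10% | 63.6% | 35.0% | 4.4% | 8.7% | 30.8 |

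Example, second row: (36 × 0.6 + 20 × 0.6)/(36 + 20 × 0.6) = 33.6/48 = 70.0%. Neither histology-only reference gives a sensitivity above 60% in any row, so every rejection is false under both.

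The simulation uses a latent correlation of 0.925. This gives a correlation of 0.75 between cytology results when both rates are 60%. In mixed pairs it gives about 0.53 at q = 30% and 0.27 at q = 10%.

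**Size, specificity.** Assume C = 200 and D = 20. The last two columns set s at the 70% null, where exact rejection at D = 0 is 2.5%.

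| q | As written, s = 90% | Composite | Tube only | Exact rejection, s = 70% | Tube-only truth, s = 70% |
|---|---|---|---|---|---|
| 60% | 90.4% | 90.0% | 85.5% | 4.5% | 67.3% |
| 30% | 90.7% | 90.0% | 88.2% | 7.8% | 70.0% |
| 10% | 90.8% | 90.0% | 90.0% | 10.5% | 71.8% |

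These rejections are false against the composite, where specificity is 70%. Against tube-only histology they are false only at q = 60% and 30%.

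**The case against.** **Another reading.** The involvement definition and section 4 might make every tube beside a malignant ovary positive. The cytology-negative counterpart would then be a false negative and the inflation would be zero. The primary comparator, ovaries and tube together, lends this some support. But the definition says only that ovarian histology can detect migration, and section 4 uses the ovaries only where migration occurred, without saying how that is established when the tube is negative. On this reading the cytology condition has no effect and should be deleted, so the text needs amending either way.

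**A third coding.** The counterpart could be left out of both measures. The specificity gain over the composite then disappears, but the sensitivity inflation remains. The specificity figures therefore need true-negative coding, and at an expected 90% the shift from the composite is only 0.4 to 0.8 points.

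**Few such tubes.** Section 6.2 expects washout only in some cases. Exact rejection at q = 60/30/10% is 2.7/2.3/1.7% for D = 3 and 3.7/2.6/2.2% for D = 5. Section 1.3 reports 95% agreement between cytology and tube histology in an earlier study. Carried over loosely, that allows about 0.05 × 280 = 14 discordant tubes, fewer than the 28 × 0.6 = 16.8 in the most extreme row. This stands as a limit on size. The same study reported 100% sensitivity and specificity for involvement despite that 95%, which suggests, without proving, that the two measures can diverge.

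**The planned analysis was not simulated.** The primary method is a logistic random-effects model; "The adjustment proposed by Obuchowski will be performed for comparison". That is correct, and the 3.9% at D = 0 is not due to this rule. Still, a clustering model takes the classified tubes as given and cannot undo the classification.

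**Mitigation.** The rule is prespecified and explained, and the secondary analyses will show much of its effect. They do not protect the primary tests. Recruitment under section 6.4 is governed by 32 and 18 subjects classed by histology, so cytology does not drive that rule. It does affect how many tubes count as positive towards 56.

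**Conclusion.** The concern holds. Positive cytology is part of the primary reference classification, and the counterpart case is unclassified; both follow from the text alone. On the plain reading the bias can only favour the device, in both primary measures, and the 2.5% error rates are not assured.

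The size is conditional. Over the tabulated assumptions, exact false success on sensitivity runs from 2.2% to 49.0%, against 1.4% without such tubes. It is near or below nominal when they are few or seldom cytology-positive. The specificity effect is smaller and depends on coding the counterpart as a true negative. The number of such tubes and their positive rate are assumptions, and the random-effects model itself was not evaluated. This must be fixed before results are compared, because a reference standard chosen afterwards would not be credible.

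**What to change.** Replace the exception in section 6.2 with one reference classification for every tube, from histology alone and fixed before the comparison with cytology. Two choices are open to the sponsor:

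- **Composite:** tube or same-side ovary malignant means positive. The cytology-negative counterpart is then a false negative.
- **Tube only:** tube histology decides. The cytology-positive tube beside a malignant ovary is then a false positive.

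Print the full table of tube histology, ovarian histology and cytology combinations with the class of each. Use the chosen reference for the 60% and 70% tests and for all involvement-based secondary and subject-level analyses. Report the other as a sensitivity analysis, and keep favorable discordance only as a labelled exploratory result.

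The cost is a protocol amendment. No new data are needed, since tube histology, ovarian histology and cytology are already on the case report forms. Headline sensitivity, specificity or both will probably be lower, and the count towards 56 positive tubes may change. The composite may also bias sensitivity downward if some tubes beside malignant ovaries hold no malignant cells.
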